13.2.3 DTC Assessment by Fluorescence-Activated Cell Sorting (“DTC-Flow”)

For the DTC-Flow assay, a bone marrow aspirate sample drawn from the iliac crest under anesthesia will be collected in an anti-coagulated tube containing EDTA and stored at room temperature until DTC-Flow processing (within 48 hours of sample collection). Bone marrow aspirates will be processed for flow cytometric analysis using a stain-lyse-no wash protocol in which samples are first stained with

fluorescently-conjugated antibodies recognizing a panel of DTC markers, along with the hematopoietic cell marker CD45. Bone marrow aspirates will be incubated with magnetic particles conjugated to antibodies against CD45, enabling the depletion of CD45-positive bone marrow cells, and then subjected to red blood cell lysis and DAPI staining to distinguish live versus dead cells. DTCs will be detected by flow cytometry on a fluorescence-activated cell sorter (FACS). DTCs will be identified as DAPI-negative (live), CD45-negative (non-hematopoietic) cells that are positive for expression of one or more DTC markers, and sorted for downstream genomic analyses. Standardization of cytometry and sorting parameters will be performed using defined fluorescent particles, allowing the use of consistent sorting gates established through the analysis of multiple stained bone marrow aspirates collected from healthy donors.

A variety of methods have been developed for single cell genomic analysis, and this field is rapidly evolving. Below, we have prioritized technical approaches, however these choices would be modified and updated according to technical developments in the field¹¹⁶⁻¹²⁹.

DTC allocation to produce pooled biological replicates: To mitigate the effect of amplification on library complexity resulting from sampling drop-out, DTCs isolated from patients by DTC-Flow will be allocated to 9 different pools of DTCs (3 pools for RNA-seq; 3 pools for WES, and 3 pools for aCGH). Each pool will be amplified and sequenced separately. For patients with fewer than 9 DTCs, priority will be given to pools allocated for WES and aCGH.

RNA-seq: The three pools of DTCs allocated to RNA-seq will be sequenced using SMART-seq2 methodology¹³⁰, which enriches, amplifies, and processes polyadenylated transcripts into libraries for RNA-sequencing in one pipeline. SMART-Seq v4 Ultra Low Input RNA Kits are commercially available (Illumina) and are compatible with HiSeq 4000 sequencing. Resulting non-zero normalized read counts will be averaged across pools and used as features for gene expression analyses.

WES: DTC pools allocated to WES will be whole-genome amplified using multiple-displacement-amplification (MDA), which has been demonstrated to produce libraries with high coverage (>90%) across the targeted exome, with fewer false positives resulting from amplification errors than other methods¹³¹. Following amplification, libraries will be constructed using the SureSelect v5 Library Preparation kit. Libraries will be sequenced on the HiSeq 4000 with 150 bp paired-end reads (150PE). Only SNV calls that are present in at least two pools will be considered as true positives.

CNV: DTCs pools allocated to aCGH will be whole-genome amplified using multiple annealing- and looping-based amplification cycles (MALBAC). MALBAC produces a more uniform distribution of coverage across the genome, thus making it more suitable for CNV assays than amplification from MDA¹³². DNA will be hybridized to SurePrint G3 Human 4 x 180k aCGH arrays. Resulting signals will be segmented and compared among the three pools to identify true positive CNAs.

Residual tumor genomics: RNA-seq, WES and aCGH on residual tumor specimens will be performed as described in 2.3.1.

Circulating tumor genomics: Genomic analysis of CTCs and ptDNA will be performed as previously described.

13.2.4 ptDNA Analysis

2 10 ml blood samples will be obtained for ptDNA at each time point per the study calendar. Plasma will be processed within 2 hours of collection using our standard protocol and stored until ready for use. Preparation of plasma within 1 to 2 hours of venipuncture is a critical parameter for maintaining high quality plasma DNA¹³³. Streck tubes (Cell-Free DNA BCT) for blood collection will be used, as we have recently published the ability of this tube to store blood samples at room temperature for up to 7 days without loss of plasma DNA integrity¹³⁴.

13.2.5 CTC analysis

Two 10 mL whole blood samples will be collected in EDTA Blood Collection Tubes at each time point per the study calendar. Buffy coat will be processed within 2 hours of collection using our standard protocol. Cytospin slides will be prepared with 1 million cells per slide for immunofluorescent staining. The remaining cells will be frozen as indicated in the standard processing protocol. The markers used for CTC identification will include CD49c, CK, EpCAM, and HER2. CD45 will be used to distinguish WBCs (CD45 positive) from CTCs (CD45 negative).

13.3 Genetic Testing

Participants will be given information as part of the informed consent process that samples will be used for research tests that will include genetic studies and testing. The intent is not to give participants (or his/her medical providers) the results of any testing done for research purposes; however, incidental germline (heritable) mutations may be identified of which a participant may or may not already be aware. In the case that an incidental genetic finding is identified, the Protocol Chair of this project will be notified. The possible decisions for handling incidental findings may include notification of the participant (and provider); recommendation for genetic counseling, which may or may not include genetic testing (e.g., if the finding was not done in a CLIA certified laboratory); or, neither. In general, a member of the participant's treating team will be given the information to help with notification. In all cases, the current policy of the University of Pennsylvania and local/participating site IRB, as applicable, will be followed and any additional approvals that may be required prior to participant notification will be secured in advance.

14 DATA HANDLING AND RECORD KEEPING

14.1 Confidentiality

Information about study patients will be kept confidential and managed according to the requirements of the Health Insurance Portability and Accountability

Act (HIPAA). Those regulations require a signed patient authorization informing the patient of the following:

- What protected health information (PHI) will be collected from patients in this study
- Who will have access to that information and why
- Who will use or disclose that information
- The rights of a research patient to revoke their authorization for use of their PHI.

In the event that a patient revokes authorization to collect or use PHI, the investigator, by regulation, retains the ability to use all information collected prior to the revocation of patient authorization. For patients that have revoked authorization to collect or use PHI, attempts should be made to obtain permission to collect at least vital status (i.e. that the patient is alive) at the end of their scheduled study period.

14.2 Source Documents

Source data is all information, original records of clinical findings, observations, or other activities in a clinical trial necessary for the reconstruction and evaluation of the trial. Source data are contained in source documents. Examples of these original documents, and data records include: hospital records, clinical and office charts, laboratory notes, memoranda, evaluation checklists, pharmacy dispensing records, recorded data from automated instruments, copies or transcriptions certified after verification as being accurate and complete, x-rays, and patient files.

14.3 Case Report Forms

The study case report form (CRF) is the primary data collection instrument for the study. All data requested on the CRF must be recorded. All entries will be entered into an electronic data capture system (EDC) via Oracle Clinical. Mandatory CRFs used for reporting to the ACC DSMC will be entered into Penn CTMS/VELOS.

15 STUDY FINANCES

15.1 Funding Source

This trial will be funded via the 2-PREVENT Breast Cancer Translational Center of Excellence and the NIH Research Project Grant: R01-CA208273. Novartis will provide commercial EVE to study participants. The DOD will support some of the correlative research using samples collected as part of this study.

15.2 Conflict of Interest

None to declare.

15.3 Patient Stipends or Payments

Patients will not be paid for participating in this clinical trial. However, assistance may be provided with parking and transportation and the costs of non-standard tests.

16 GENERAL REGULATORY CONSIDERATIONS AND CREDENTIALING

16.1 Publication of results

Any formal presentation or publication of data from this trial may be published after review and comment by Novartis and prior to any outside submission. Novartis

must receive copies of any intended communication in advance of publication (at least fifteen working days for presentational materials and abstracts and thirty working days for manuscripts). These requirements acknowledge Novartis' responsibility to provide peer input regarding the scientific content and conclusions of such publications or presentations. Principal Investigation/Institution shall have the final authority to determine the scope and content of its publications, provided such authority shall be exercised with reasonable regard for the interests of Novartis and, in accord with the trial contract and shall not permit disclosure of Novartis confidential or proprietary information.

16.2 Disclosure and confidentiality

The investigator agrees to keep all information provided by Novartis in strict confidence and to request similar confidentiality from his/her staff and the IRB/IEC/REB. Study documents provided by Novartis (investigators' brochures and other material) will be stored appropriately to ensure their confidentiality. The information provided by Novartis to the investigator may not be disclosed to others without direct written authorization from Novartis, except to the extent necessary to obtain informed consent from patients who wish to participate in the trial.

16.3 Ethics and Good Clinical Practice

This study must be carried out in compliance with the protocol and the principles of Good Clinical Practice, as described in Novartis standard operating procedures and:

- ICH Harmonized Tripartite Guidelines for Good Clinical Practice 1996. Directive 91/507/EEC, The Rules Governing Medicinal Products in the European Community.
- US 21 Code of Federal Regulations dealing with clinical studies (including parts 50 and 56 concerning informed consent and IRB regulations). Declaration of Helsinki and amendments, concerning medical research in humans (Recommendations Guiding Physicians in Biomedical Research Involving Human Subjects).

The investigator agrees to adhere to the instructions and procedures described in it and thereby to adhere to the principles of Good Clinical Practice that it conforms to.

16.4 Institutional Review Board/Independent Ethics Committee

Before implementing this study, the protocol, the proposed informed consent form and other information to subjects, must be reviewed by a properly constituted Institutional Review Board/Independent Ethics Committee/Research Ethics Board (IRB/IEC/REB). A signed and dated statement that the protocol and informed consent have been approved by the IRB/IEC/REB must be given to Novartis before study initiation. Any amendments to the protocol, other than administrative ones, must be reviewed by Novartis approved by this committee.

16.5 Informed consent

The investigator must explain to each subject (or legally authorized representative) the nature of the study, its purpose, the procedures involved, the expected duration, the potential risks and benefits involved and any discomfort it may entail. Each subject must be informed that participation in the study is voluntary and that he/she may withdraw from the study at any time and that withdrawal of

consent will not affect his/her subsequent medical treatment or relationship with the treating physician.

This informed consent should be given by means of a standard written statement, written in non-technical language. The subject should read and consider the statement before signing and dating it, and should be given a copy of the signed document. If the subject cannot read or sign the documents, oral presentation may be made or signature given by the subject's legally appointed representative, if witnessed by a person not involved in the study, mentioning that the patient could not read or sign the documents. No patient can enter the study before his/her informed consent has been obtained.

The informed consent form is considered to be part of the protocol, and must be submitted by the investigator with it for IRB/IEC/REB approval.

#### Bayesian Poisson regression model

The number of DTCs observed by visit for each patient was analyzed with a Bayesian Poisson regression model that included treatment-by-visit effects and patient-level random intercepts to account for overdispersion in the outcomes. We denote observations within index  $i \in 1, ..., N$  and patients with index  $s[i] \in 1, ..., S$ . Let  $y_i$  represent the number of DTCs for observation i. The Bayesian model is specified as follows:

$$y_i \sim Pois(\lambda_i)$$
  
 $\log(\lambda_i) = \alpha + \mu_{s[i]} + X'_i \beta$ 

where  $\alpha$  is an overall intercept,  $\mu_{s[i]}$  is a patient-level intercept,  $X_i$  is a vector of treatment by visit effects, and  $\beta$  is a vector of treatment effects by visit. The following non-informative prior distributions are specified on the unknown model parameters:

$$\alpha \sim N(0, 10^2)$$
  
 $\beta_j \sim N(0, 10^2), j = 1:j$   
 $\mu_s \sim N(0, \sigma^2), s = 1:S$   
 $\sigma \sim t_3^+(0, 1)$ 

Posterior sampling was done using the *brms* package (version 2.19.0) in the R programming language (version 4.3.1). Treatment effects for HCQ, EVE, and HCQ + EVE are presented by visit as the percent reduction in mean DTCs compared to observation alone at C3. Combination effects are evaluated by comparing the mean number of DTCs with HCQ + EVE to HCQ and EVE alone by visit. The estimated probability of DTC clearance is presented by visit and treatment group. Summaries of model parameters include the posterior mean, median, standard deviation (SD), and 95% credible interval (CrI).

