5.2 Screening Phase

Patients found to have detectable DTCs by immunohistochemistry, through the PENN-SURMOUNT Screening study (UPCC 28115; IRB# 824098) or other studies will be screened for trial participation during the screening phase. This will include assessments of medical history, overall physical condition, physical exam, baseline laboratory studies, and symptom-directed imaging (if applicable) to rule out the presence of overt metastatic disease, per NCCN guidelines. Patients will undergo a baseline bone marrow aspirate if their prior bone marrow aspirate detecting DTCs occurred > 6 months prior to the screening phase. If a bone marrow aspirate positive for DTCs occurred ≤ 6 months prior to screening, this will not be repeated, and the prior DTC count will provide the baseline DTC assessment.

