7 TREATMENT PLAN

This is a randomized, controlled, open label pilot trial. A total of 60 patients

will be enrolled, with at least 15 patients allocated to each treatment group (Arms C and D constituting the same treatment group). The initial treatment period is 6 months (24 weeks). During the initial treatment period, patients will be randomized to one of 4 arms: HCQ alone (Arm A), EVE alone (Arm B), combination HCQ and EVE (Arm C) – Arm C is closing to accrual with Amendment 7 – or control/delayed combination HCQ and EVE (Arm D). Starting with Amendment 7, patients who would have been allocated to Arm C will be redirected to Arm D in order to increase the number of patients with repeat DTC assessments to aid assay reproducibility analysis. At the conclusion of 3 cycles of therapy (Arms A, B, and C) or 3 cycles of observation (Arm D), patients will undergo repeat bone marrow aspirate. Patients on Arm D will then commence combination therapy with HCQ + EVE for 6 cycles (24 weeks). After 3 cycles of therapy, patients on Arm D will undergo another bone marrow aspirate. After 6 cycles of therapy, patients on all arms will undergo another bone marrow aspirate. Patients with a negative bone marrow aspirate for DTCs at after cycle 6 will have all therapy discontinued and enter the follow up phase. Patients who have persistently positive bone marrow DTCs will be continued on combination HCQ + EVE for an additional 6 cycles (24 weeks). At the conclusion of this combination treatment period (cycle 12), all treatment will be discontinued and a bone marrow aspirate will be performed.

Patients will be evaluated at the initiation of every cycle for adverse events, and dose reductions will be employed for toxicity. Patients will continue to be followed for recurrence events for 3 years after completion of treatment.

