11.1.3 Measurable Disease

Patients enrolled on the CLEVER trial will have completed surgery for their primary breast tumor and be free of overt metastatic disease. Thus there is no tumor to measure for the effect of the study therapy. Rather, the goal of this trial is to eradicate minimal residual disease, in the form of disseminated tumor cells (DTCs) that are present in the bone marrow. Therefore, bone marrow DTCs constitute the "measurable" disease in this trial. A patient will be classified as having "measurable disease" if at least 1 disseminated tumor cell (DTC) is detected

in 5 ml of bone marrow aspirate by immunohistochemistry, as described in section 13.2.1.

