12 STATISTICAL CONSIDERATIONS AND METHODOLOGY

12.1 Sample Size

The primary endpoint of this pilot study is feasibility. 60 patients will be enrolled on the trial. Based on the literature and our preliminary experience, we anticipate detecting BM-DTCs in 20 - 25% of the patients we screen on the PENN-SURMOUNT study (IRB# 824098/UPCC 28115), thus have planned to screen 250 - 300 patients over three years, allowing for refusals and drop-out.

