12.2.2 Secondary Endpoints

The secondary endpoints are tolerability/toxicity and the measured effect of the investigational therapy on DTCs in patients with measureable DTCs at baseline and the comparison of this effect to that in a control population. Because this is proof-of-concept, sample sizes are not sufficient to address long-term recurrence risk. Randomization is being performed to minimize uncontrolled confounding.

We will define “response” for each patient as a 50% or greater decrease in DTC number at each treatment time point compared to baseline. A treatment arm will be considered successful if at least 3 of 15 patients experience this predefined response endpoint. This strategy is being used to provide preliminary estimates of effect on DTCs and to assess whether one or more treatment approaches has sufficient activity to be considered in a larger study powered for relapse-free survival. We anticipate that the baseline variability in DTC measurement will lead to no more than a 4% response rate in the absence of treatment (null rate). While the trial is powered for feasibility, 15 patients provide approximately 80% power to detect a response rate of 20%, warranting further study of the treatment strategy evaluated in this patient population and clinical setting.

We will also estimate, within each treatment group, the % change in BM-DTC number, defined as the difference between BM-DTCs enumerated at 6 months and at baseline, divided by the number at baseline; we will compare this quantity across treatment groups using simple regression analyses with indicator variables for the three active treatments compared to the delayed treatment. While the trial is powered for feasibility, rather than detection of change in BM-DTCs across treatment group, 15 patients per group will provide 80% power (using a two-group t-test with a two-sided alpha level of 0.05) to detect a decrease in BM-DTCs of approximately 1 standard deviation between any two groups and will provide important preliminary data for designing future trials.

Because of tumor heterogeneity, the natural history of recurrence varies substantially between breast cancer subtypes. We have elected not to expand the

sample size to evaluate subtypes individually in this feasibility pilot, but expect that we will enroll a mix of patients across subtypes that will shed light on variability in DTCs by subtype in an exploratory fashion.

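### The SAP's patient-level intercepts cover only differences in level between patients; if DTC counts vary within patients beyond Poisson, or patients respond unequally, the 95% credible intervals can be too narrow, most robustly for HCQ + EVE versus observation

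*SAP*

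**What the plan says.** The SAP (Bayesian Poisson regression model) states: "The number of DTCs observed by visit for each patient was analyzed with a Bayesian Poisson regression model". The linear predictor is an overall intercept, one intercept per patient drawn from N(0, σ²), and treatment-by-visit effects. The stated purpose of the patient term is given in the words "patient-level random intercepts to account for overdispersion in the outcomes". Effects are reported by visit as percent reductions against observation at C3 and as combination-versus-single-agent comparisons, with 95% credible intervals. The section lists no dispersion parameter, observation-level effect, random slope, predictive check or alternative count model. It does not say whether baseline counts are modelled or, if they are, whether baseline is one cell for all arms or one per arm.

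The protocol bears on the counts in several places:

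- Measurable disease is present "if at least 1 disseminated tumor cell (DTC) is detected" (11.1.3), so baseline has no zeros.
- When a positive aspirate is no more than 6 months old at screening, "the prior DTC count will provide the baseline DTC assessment" (5.2).
- Section 12.1 says "we anticipate detecting BM-DTCs in 20 - 25% of the patients we screen".
- Section 12.2.2 assumes that "baseline variability in DTC measurement will lead to no more than a 4% response rate in the absence of treatment".
- Section 7 redirects Arm C patients to Arm D to "increase the number of patients with repeat DTC assessments to aid assay reproducibility analysis".

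**The concern.** A patient intercept takes the same value at every visit. It explains why one patient's counts are all high and another's all low. It cannot explain why one patient's counts move between visits by more than Poisson noise, or why some patients respond and others do not. Contrasts made largely within patients are exposed to exactly that unmodelled variation.

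The protocol makes such variation plausible without showing it. Assay reproducibility is still to be analysed, extra slides are prepared for atypical or indeterminate samples (13.2.1) with no offset in the model, the baseline marrow can be months old, and response is judged patient by patient.

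The reductions versus observation and the combination contrasts are meant to inform a larger trial. If the extra variation exists, they may look more precise than the data allow.

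**Working it through.** **No stated figure to reproduce.** The documents give no interval width, dispersion or count distribution. All counts and CVs below are assumptions, shown as ranges.

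**Variance.** If a patient's visit mean λ is multiplied by noise with coefficient of variation c, the count variance given the patient is λ + λ²c². The SAP model allows λ. The SD is therefore understated by the factor √(1 + λc²). At c = 0.5:

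- λ = 0.29: √(1 + 0.0725) = 1.04
- λ = 5: √(1 + 1.25) = 1.50
- λ = 15: √(1 + 3.75) = 2.18

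The effect is negligible at low counts and large at high ones.

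**Count scenarios** (means before selection on a baseline of at least 1):

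- (a) Low, light-tailed: log-normal patient SD 0.9, mean 0.29, giving about 22.5% detection as in 12.1.
- (b) Same detection, heavy-tailed: log-normal SD 2, mean 0.73.
- (c) Mean 5, log-normal SD 0.9. This implies 83-89% detection, so it fits 12.1 only if most screened patients carry no DTCs.

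**Coverage by baseline coding.** SAP model and priors; 15 patients per arm; visits baseline, C3 and C6, plus observation C3 in Arm D. Visit CV 0.5, 160 simulated trials per cell, interval = posterior mode ± 1.96 posterior SD. For a single contrast the Monte Carlo error is √(0.8 × 0.2/160) = 3.2 points at 80% coverage.

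| Contrast | Scenario | Pooled baseline | Arm-specific baseline | No baseline |
|---|---|---|---|---|
| HCQ or EVE vs observation | (b) | 80% | 85% | 92% |
| HCQ or EVE vs observation | (c) | 81% | 89% | 92% |
| Combination vs single agent | (b) | 81% | 88% | 93% |
| Combination vs single agent | (c) | 79% | 90% | 92% |
| HCQ + EVE vs observation | (b), (c) | 78-80% | 78-80% | 78-80% |

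With a pooled baseline the single-agent contrasts are in effect within-patient. Without one they are largely between-patient, and the fitted patient variance already widens the interval. HCQ + EVE versus observation is exposed under every coding because Arm D patients supply both cells.

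**Negative binomial refit, pooled baseline only** (Hamiltonian Monte Carlo, 160 trials per cell). Figures are coverage of all treatment-versus-observation contrasts / combination-versus-single-agent contrasts.

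| Scenario, CV | Poisson | Negative binomial | Extra width |
|---|---|---|---|
| (a), 0 | 90/91% | 90/91% | 1% |
| (a), 0.5 | 87/88% | 87/89% | 1% |
| (b), 0 | 90/90% | 93/92% | 7% |
| (b), 0.5 | 78/74% | 89/88% | 21% |
| (c), 0 | 95/94% | 96/95% | 8% |
| (c), 0.5 | 77/81% | 94/94% | 40% |

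In (a) extra variation costs about 3 points and the refit changes almost nothing. Most of that shortfall is present at CV 0, because baseline is selected to be at least 1. Unequal response in (b) (log-SD 0.7, no visit noise) gives 81/75% under Poisson and 91/90% under negative binomial. With 5 patients in Arm C and 25 in Arm D, an assumed split after Amendment 7, (b) at CV 0.5 gives 75/78% and 90/88%.

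**Does the 4% null rate settle it?** Under pure Poisson with no change, the probability of a fall of at least 50%, given a baseline of at least 1, is 53% at mean 1, 28% at mean 3, 8% at mean 10 and 4.2% at mean 15. So 4% requires patient means of about 15 or more. With added visit variation it requires means of about 18, 22, 33 and 90 at CV 0.1, 0.15, 0.2 and 0.25, and it cannot hold at CV 0.28 or above. A simple within-patient comparison of arm totals has coverage of 93, 90, 83 and 60% at those four points.

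**The case against.** The strongest reply has four parts.

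*The SAP sentence is not false.* Patient intercepts do model marginal overdispersion, and Poisson against negative binomial is a modelling choice. This stands as far as it goes: the sentence is incomplete, and the part it leaves out matters for within-patient contrasts.

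*Large losses rest on assumptions about baseline coding.* This stands. With arm-specific or absent baseline cells, the single-agent and combination-versus-single-agent intervals lose much less. What remains under every coding is HCQ + EVE versus observation.

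*With low, light-tailed counts the refit does nothing.* This also stands, and it is why the point is conditional.

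*The 4% null rate limits the extra variation.* Taken at face value it excludes the CV of 0.5 used above. But it also requires means of about 15 or more, where a CV of 0.2 to 0.25 already does damage in the simple within-patient comparison. If counts are lower, the 4% cannot hold and says nothing about dispersion.

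A reader might infer that an apparent benefit under the SAP model would vanish under a negative binomial model. The documents do not support that. In (b) at CV 0.5 the median posterior SD for HCQ or EVE versus observation is about 0.48 with arm-specific baselines and 0.63 with none. For a 50% reduction, 1 − 0.5·exp(±1.96 × 0.48) gives −28% to 80%, and 0.63 gives −72% to 85%. Under those codings the Poisson interval already includes no effect.

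**Conclusion.** The structural point holds: the intercepts cover between-patient differences in level only, and the model has no term for within-patient extra-Poisson variation or unequal response. Whether the reported intervals are in fact too narrow cannot be told from the documents. A reader might infer that the counts are overdispersed or that all intervals are badly wrong; neither is shown.

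Under assumed heavy-tailed counts or a mean of 5, with a visit CV of 0.5, coverage of nominal 95% intervals is about 78-80% for HCQ + EVE versus observation under all three codings. For the other contrasts it is 79-81% with a pooled baseline, 85-90% with arm-specific baselines and 92-93% with no baseline. With low, light-tailed counts the loss is at most a few points. These figures assume 15 patients per arm, which Amendment 7 changes for Arms C and D.

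The reach is limited to secondary results. The feasibility endpoint and the 3-of-15 response rule do not use this model. Nor does the percent-change analysis in Protocol 12.2.2 ("we will compare this quantity across treatment groups using simple regression analyses"), which estimates its own residual variance. A sensitivity analysis should be added; confidence in its practical effect is medium.

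**What to change.** 1. State whether baseline counts enter the model and, if so, whether as one pooled cell or one per arm.
2. Beside the Poisson result, refit the same brms model with `family = negbinomial()` or an observation-level random effect, using the same visits. Report every contrast under both models, giving most attention to HCQ + EVE versus observation.
3. Add a posterior predictive check of within-patient variance and zero fraction on post-baseline visits, since baseline has no zeros by selection. Show both models whatever it says: a Pearson-type check flagged CV 0.5 in 86% of trials in (c) but only 7% in (b).
4. Do not estimate dispersion from Arm D's baseline and end-of-observation pair alone. Selection biases it downwards (0.80-0.82 instead of 1 at mean 0.3 under pure Poisson).
5. Reword the sentence to say that the intercepts cover between-patient variation only.

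The cost is one model term, a rerun and somewhat wider intervals: about 1-8% with no extra variation and up to about 40% at CV 0.5, in the pooled-baseline runs. The SAP is written in the past tense, so the refit is shown beside the Poisson analysis and does not replace it.
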